## ABBREVIATIONS

CT	Computed tomography
DCE-MRI	Dynamic contrast enhanced magnetic resonance imaging
ER	Estrogen receptor
FDA	U.S. Food and Drug Administration
FDG	$^{18}\text{F}$ -fluorodeoxyglucose
FFNP	$^{18}\text{F}$ -fluorofuranyl norprogesterone
HER2	Human epidermal growth factor receptor 2
IHC	Immunohistochemistry
IRB	Institutional review board
mCi	MilliCurie
MIRS	Medical Imaging Research Support
MRI	Magnetic resonance imaging
PACS	Picture archiving and communication system
PET	Positron emission tomography
PR	Progesterone receptor
ROC	Receiver operating characteristic
ROI	Region of interest
SUV	Standard uptake value
UW	University of Wisconsin

## 1. PROTOCOL SUMMARY

### TITLE OF STUDY

[F]FluorofuranylNorprogesterone (FFNP) PET/MR Imaging of Progesterone Receptor Expression in Invasive Breast Cancer

### CLINICAL PHASE

Phase 2

### PERIOD OF TRIAL

Planned study conduct duration of approximately 36 months.

### STUDY OBJECTIVES

Integrated whole-body magnetic resonance imaging (MRI)-positron emission tomography (PET) scanners have recently been introduced for clinical use. This technology combines the anatomic and perfusion data obtained with dynamic contrast enhanced (DCE) MRI with functional imaging data obtained from PET. For breast imaging, the combination of MRI and PET has important potential to improve diagnostic accuracy and provide molecular characterization of breast cancer. The overall purpose of this research is to test the accuracy of PET/MRI imaging with F-fluorofuranylNorprogesterone (FFNP) for measuring progesterone receptor (PR) expression in patients with invasive breast cancer.

#### Primary Objective

To compare FFNP uptake of biopsy-proven primary PR+ breast malignancies measured using PET/MRI with the reference standard of PR immunohistochemistry (IHC).

#### Secondary Objectives

1) To determine the test-retest reproducibility of quantitative assessment of tumor FFNP uptake; 2) to determine the intra- and inter-observer variability of quantitative assessment of tumor FFNP; 3) to evaluate the optimal cut-point of FFNP uptake for distinguishing between PR-negative and PR-positive invasive breast cancer; and 4) estimate the association of tumor FFNP uptake (continuous SUVmax) with research-based Oncotype DX scores (0-100).

#### Exploratory Objectives

1) To evaluate heterogeneity of tumor FFNP uptake; 2) to correlate tumor FFNP uptake with serum progesterone and estradiol levels; and 3) to correlate tumor FFNP uptake with disease recurrence.

## INCLUSION CRITERIA

- Women 18 years of age or older
- Diagnosis of biopsy-proven invasive breast cancer measuring at least 1.0 cm in diameter by any imaging modality
- Biopsy-proven PR-positive) or PR-negative invasive breast cancer
- Undergoing diagnostic breast MRI ordered by the referring clinician for staging and extent of disease\*

## EXCLUSION CRITERIA

- Inability or unwillingness to provide informed consent to the study
- Patients who have had neoadjuvant chemotherapy/endocrine therapy, surgical intervention, or radiation for the current biopsy-proven malignancy
- Patients with breast expanders
- Patients who are or might be pregnant or lactating
- Patient girth exceeds the bore of the PET/MRI scanner
- Patients with a contraindication to gadolinium based contrast agents, including allergy or impaired renal function (per UW Health Guidelines)
- Patients with a history of allergic reaction attributable to compounds of similar chemical or biologic composition to FFNP
- Patients in liver failure as judged by the patient's physician
- Patients with standard contraindications to MRI, including claustrophobia and metallic implants incompatible with MRI
- Patients requiring intravenous (IV) conscious sedation for imaging are not eligible; patients requiring mild, oral anxiolytics for the clinical MRI will be allowed to participate as long as the following criteria are met:
  - The subject has their own prescription for the medication
  - The informed consent process is conducted prior to the self-administration of this medication
  - They come to the research visit with a driver
- Patients unable to lie prone for 30 minutes for imaging

## STUDY DESIGN

This is a prospective, one-arm, study which will enroll patients with newly diagnosed breast cancer scheduled for diagnostic breast MRI for preoperative staging/extent of disease evaluation as part of standard of care. Eligible patients will be consented for participation in the research study which includes a directed breast PET/MRI with the investigational radiopharmaceutical, FFNP. FFNP uptake of the known, biopsy-proven malignancy will be measured using standardized uptake values (SUV) and tumor-to-normal tissue ratios. The proposed work-flow is described in the schema below.

## NUMBER OF SUBJECTS

---

[figure not shown]
\* Patients with newly diagnosed invasive breast cancer from a screening breast MRI are eligible to participate in this research. For these subjects, the research breast PET/MRI should be performed prior to any treatment or surgery for the invasive breast cancer.

The primary objective is to compare FFNP  $SUV_{max}$  from PET/MRI with the PR immunohistochemistry semi-quantitative score obtained by using the Allred score (0-8) (1). The correlation of the two measures will be evaluated with Pearson's correlation coefficient. The null hypothesis is  $H_0: p_0=0.20$  and the alternative hypothesis is  $H_1: p_1=0.70$ .

A sample size of 21 patients achieves 80% power to detect this difference, using a one-sided hypothesis test with a Type I error of 5%, accounting for 1 dropout. Up to 5 subjects with PR-negative breast cancer will be enrolled.

To measure test-retest reproducibility, a subset of up to 5 PR+ participants will have test-retest FFNP scans.

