## 12. STATISTICAL CONSIDERATIONS

### 12.1 Primary Objective

12.1.1 To compare FFNP uptake of biopsy-proven primary PR+ breast malignancies measured using PET/MRI with the reference standard of PR immunohistochemistry (IHC).

The primary objective is to compare FFNP  $SUV_{max}$  from PET/MRI with the PR immunohistochemistry semi-quantitative score obtained by using the Allred score (0-8) (1). The correlation of the two measures will be evaluated with Pearson's correlation coefficient. The null hypothesis is  $H_0: p_0=0.20$  and the alternative hypothesis is  $H_1: p_1=0.70$ .

A sample size of 21 patients achieves 80% power to detect this difference, using a two-sided hypothesis test with a Type I error of 5%, accounting for 1 dropout. Sample size calculations were done in PASS 14 (NCSS, LLC, Kaysville, Utah. <http://www.ncss.com>).

Other measures of FFNP uptake including  $SUV_{peak}$  (small fixed-size ROI centered on most metabolically active part of tumor),  $SUV_{mean}$  (average value), tumor-to-normal tissue uptake ratio, and total lesion uptake (functional tumor volume  $\times$   $SUV_{mean}$ ) will also be correlated with the PR immunohistochemistry semi-quantitative score obtained by using the Allred score.

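### The primary correlation test is one-sided 5% in the Protocol Summary and two-sided 5% in Section 12.1.1; 21 patients for 80% power fits only the two-sided version

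*Combined protocol and SAP*

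**What the plan says.** The primary test is described twice in the combined protocol and SAP.

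- Protocol Summary, Number of Subjects: 80% power with 21 patients, "using a one-sided hypothesis test with a Type I error of 5%, accounting for 1 dropout".
- Section 12.1.1: the same power and the same number of patients, but here "using a two-sided hypothesis test with a Type I error of 5%, accounting for 1 dropout".

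The rest is the same in both places. The endpoint is SUVmax against the Allred score, and the statistic is fixed: "The correlation of the two measures will be evaluated with Pearson's correlation coefficient". The null correlation is 0.20 and the alternative 0.70. Only Section 12.1.1 names the software ("Sample size calculations were done in PASS 14"), and it does not say whether an exact or a Fisher z procedure was used. Neither section gives a critical value of r, a p-value rule or a confidence-bound rule for success, and no text gives one section precedence.

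**The concern.** One test cannot be both one-sided and two-sided at 5%. The two statements put 5% and 2.5% in the upper tail, so they set different cut-offs for the same observed correlation. They also cannot both be the basis of the same sample size: moving from two-sided to one-sided 5% either raises the power at 21 patients or lowers the number needed for 80%.

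This is the only analysis in Section 12 with stated hypotheses, error rate and power. The study is one-arm and single-institution. While both versions stand, nothing in the plan prevents the sidedness from being settled after r is known.

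**Working it through.** **Inputs.** Null 0.20, alternative 0.70, Type I error 5%, 21 enrolled and 1 dropout, all from Section 12.1.1 and repeated in the Summary. Evaluable n = 21 − 1 = 20. Bivariate normality is assumed, as is usual for this calculation.

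**Exact distribution of r.** Find the critical value c with P(r > c | ρ = 0.20) = 0.025 (upper limit of the two-sided test) or 0.05 (one-sided). Power is P(r > c | ρ = 0.70). The lower tail of the two-sided test adds nothing visible to power.

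| Evaluable n | Two-sided 5%: c | Power | One-sided 5%: c | Power |
|---|---|---|---|---|
| 16 | 0.638 | 69.4% | 0.581 | 80.0% |
| 19 | 0.604 | 77.9% | 0.550 | 86.4% |
| 20 | 0.595 | 80.2% | 0.541 | 88.0% |
| 21 | 0.586 | 82.3% | 0.533 | 89.5% |

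The two-sided test reproduces the plan. Twenty is the smallest n that reaches 80%, and one dropout makes 21. One-sided, 80% is already reached at n = 16, so 17 enrolled.

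**Fisher z as a cross-check.**

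- Effect: d = atanh(0.70) − atanh(0.20) = 0.8673 − 0.2027 = 0.6646.
- Required n = ((z_α + 0.8416)/d)² + 3.
  - Two-sided: ((1.9600 + 0.8416)/0.6646)² + 3 = 20.8, so 21.
  - One-sided: ((1.6449 + 0.8416)/0.6646)² + 3 = 17.0, so 17.
- Power at n = 20 = Φ(√17 × 0.6646 − z_α).
  - Two-sided: Φ(2.740 − 1.960) = Φ(0.780) = 78.2% (79.8% with bias correction).
  - One-sided: Φ(2.740 − 1.645) = Φ(1.095) = 86.3% (87.5% with bias correction).
- Critical r at n = 20 = tanh(0.2027 + z_α/√17).
  - Two-sided: tanh(0.678) = 0.590.
  - One-sided: tanh(0.602) = 0.538.

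**Chance of landing between the two thresholds (exact, n = 20, r from 0.541 to 0.595).**

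| True correlation | P(one-sided rejects, two-sided does not) |
|---|---|
| 0.20 | 2.5% |
| 0.50 | 12.4% |
| 0.60 | 12.7% |
| 0.70 | 88.0% − 80.2% = 7.8% |

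**The case against.** The best defence is that this is a slip in a synopsis with an identifiable answer. Section 12 is the statistical section, it names the software, and its two-sided wording reproduces 21 patients. On that view the threshold is not missing; it is ambiguous between two known values, and a sensible reader would follow Section 12. That is fair as to which version was probably meant, but no rule of precedence is written down.

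The practical reach is also limited. The design has about 80% power or more on either reading, n need not change, and in most outcomes both sections give the same verdict. The results do not guide patient care (Sections 5.1 and 7). This bears on how much harm the error does, not on whether it exists.

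Two technical points stand in part:

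- A design with 88% power does, literally, achieve 80%. The exact statement is that 21 is the minimum only for the two-sided test.
- The match depends somewhat on method. Under Fisher z, 20 evaluable patients give 78.2% two-sided, just short, and the 21 required leaves no room for the dropout. The one-sided version still misses by 6 to 8 points under either method, so the inference keeps its direction.

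Finally, correcting one word does not settle every detail of the threshold. The critical r moves with the evaluable n, and Section 5.5.6 has two readers and two sessions while Section 12.1.1 does not say which SUVmax enters the test. That limits what this fix achieves; it does not excuse the contradiction.

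**Conclusion.** The concern holds. The Summary and Section 12.1.1 contradict each other on the sidedness of the primary test. At 20 evaluable patients this moves the rejection threshold from about 0.54 to about 0.59, the upper-tail error from 5% to 2.5%, and the power from 86–88% to 78–80%. An observed r of about 0.54–0.59 would change the primary conclusion; the chance of that is 7.8% if the plan's alternative is true and 12–13% if the true correlation is 0.50 to 0.60.

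That the Summary is the wrong one is an inference from the arithmetic, though a strong one. If 21 is read as the evaluable number, it is unchanged: 82.3% exact or 80.5% by Fisher z two-sided, against 89.5% or 88.0% one-sided. All figures assume bivariate normality, which an ordinal Allred score only approximates, so the thresholds should be read to two decimals.

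The correction matters despite the adequate sample size, because this is the trial's only powered test and its decision rule is credible only if fixed before the correlation is seen.

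**What to change.** In the Protocol Summary, change one-sided to two-sided so that it agrees with Section 12.1.1. In both places, state that the null value tested is 0.20, that the level is two-sided 5%, and whether the exact distribution of r or Fisher's z is used, matching the procedure run in PASS. It helps the reader to add that at 20 evaluable patients this means rejecting when r exceeds about 0.59, as an illustration that will shift with the final n.

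If a one-sided 5% test is what was intended, correct Section 12.1.1 instead and, in both places, either restate the power at 20 evaluable patients as about 86–88% or restate the enrolment needed for 80% as 17–18 including the dropout.

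The first route costs one word plus a clarifying sentence and no extra patients; its price is the stricter threshold. Either route should be completed before any correlation between SUVmax and the Allred score is computed.

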#### 3.3 Exploratory objectives:

- To evaluate heterogeneity of tumor FFNP uptake.
- To correlate tumor FFNP uptake with serum progesterone and estradiol levels.
- To correlate tumor FFNP uptake with disease recurrence.

Study duration: 36 months. Our estimated rate of accrual is 1 participant per month.

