#### 4.1 Eligibility Criteria

##### Inclusion Criteria:

- 4.1.1 Women 18 years of age or older
- 4.1.2 Diagnosis of biopsy-proven invasive breast cancer measuring at least 1.0 cm in diameter by any imaging modality
- 4.1.3 Biopsy-proven PR-positive or PR-negative invasive breast cancer
- 4.1.4 Undergoing diagnostic breast MRI ordered by the referring clinician for staging and extent of disease†

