### **5.9 Follow-Up**

Adverse events occurring within 24 hours after FFNP infusion will be recorded by the study coordinator who will contact the subject within 1 to 3 days after FFNP administration.

Diagnosis of breast cancer recurrence, established per routine clinical care, will be recorded at the conclusion of the study for those patients with follow-up information available through the electronic medical record system (minimum 1 year after primary breast surgery).

Definition of disease recurrence during follow-up will be as follows:

- **Local recurrence:** histologic evidence of ductal carcinoma in situ or invasive breast cancer in the ipsilateral breast or chest wall.
- **Regional recurrence:** cytologic or histologic evidence of disease in the ipsilateral internal mammary, ipsilateral supraclavicular, ipsilateral

- infraclavicular and/or ipsilateral axillary nodes or soft tissue of the ipsilateral axilla.
- **Distant recurrence:** cytologic, histologic, and/or radiographic evidence of disease in the skin, subcutaneous tissue, lymph nodes (other than local or regional metastasis), lung, bone marrow, central nervous system or histologic and/or radiographic evidence of skeletal or liver metastasis.

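### Does the primary correlation fall short of PR+ patients because the plan does not say whether the PR-negative patients are among the 21?

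*Combined protocol and SAP*

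**What the plan says.** The Number of Subjects section of the protocol summary states: "A sample size of 21 patients achieves 80% power to detect this difference, using a one-sided hypothesis test". Section 12.1.1 has the same sentence with the other sidedness: "A sample size of 21 patients achieves 80% power to detect this difference, using a two-sided hypothesis test". Both use a null correlation of 0.20, an alternative of 0.70, a 5% type I error and an allowance for one dropout. Neither gives the PR status of the 21.

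The summary then adds "Up to 5 subjects with PR-negative breast cancer will be enrolled", and describes the repeat-scan group separately: "a subset of up to 5 PR+ participants will have test-retest FFNP scans". Section 12.1.1 does not mention PR-negative patients. Section 4.1 admits both kinds of tumour: "Biopsy-proven PR-positive or PR-negative invasive breast cancer". Section 12.2.3 uses both in the ROC analysis.

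The formal objective (summary, Section 3.1, heading of Section 12.1.1) is limited to PR+ malignancies, and Sections 5.2 and 13.1 describe it in the same way. The paragraphs that set out the test are not so limited. The summary and the body of Section 12.1.1 correlate SUVmax with an Allred score running from 0 to 8, and the hypothesis that opens Section 3 carries no PR restriction.

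**The concern.** A primary test on PR+ tumours needs a known number of PR+ patients, and the plan states none. Someone closing enrolment could read Number of Subjects as a ceiling of 21 in all and count up to five PR-negative patients towards it. If the test were then run on PR+ patients only, it would have 16 patients, or 15 after a PR+ dropout, while the protocol still claimed 80% power. This is the trial's only powered test.

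Two other figures seem to support the smaller total. Under the summary's one-sided test, exact power reaches 80% at 16 patients, and 21 − 5 = 16. The timetable reads "Study duration: 36 months. Our estimated rate of accrual is 1 participant per month". With the one-year minimum follow-up in Section 5.9, 21 patients finish at month 21 + 12 = 33, but 26 finish at month 26 + 12 = 38.

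**Working it through.** **Inputs.** From Number of Subjects and Section 12.1.1: ρ₀ = 0.20, ρ₁ = 0.70, α = 5%, power 80%, 21 patients including one dropout. From Number of Subjects: 0 to 5 PR-negative patients.

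**Reproducing the 21, Fisher z.** n = [(z_α + z_β) / (atanh ρ₁ − atanh ρ₀)]² + 3, with atanh 0.70 − atanh 0.20 = 0.8673 − 0.2027 = 0.6646.

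- Two-sided: [(1.960 + 0.842) / 0.6646]² + 3 = 20.77, so 21 before any dropout.
- One-sided: [(1.645 + 0.842) / 0.6646]² + 3 = 17.00, so 17, or 18 with one dropout.

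**Reproducing the 21, exact distribution of r (bivariate normal, numerical integration).**

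- Two-sided: power is 77.9% at n = 19 and 80.2% at n = 20. So 20 evaluable + 1 dropout = 21, the stated figure and the stated dropout allowance together.
- One-sided: power is 80.0% at n = 16, so 17 with one dropout. At n = 20 it is 88.0%.

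Only the two-sided exact calculation returns 21 with one dropout included. It requires 20 evaluable patients in whatever group is analysed.

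**Power under each reading.** The Fisher form is Φ(0.6646 √(n − 3) − 1.960). At n = 20 this is Φ(0.6646 × 4.123 − 1.960) = Φ(0.780) = 78.2%. Ranges below run from Fisher z to exact, two-sided, with one dropout from the analysed group and five PR-negative patients enrolled.

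| PR-negative patients are | Left out of the correlation | Included in it |
|---|---|---|
| additional (26 in all) | n = 20: 78–80% | n = 25: 88–89% |
| among the 21 | n = 15: 63–66% | n = 20: 78–80% |

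Only the lower-left cell falls short, and its size depends on how many PR-negative patients enrol. With one dropout among the PR+ patients:

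| PR-negative among the 21 | PR+ evaluable | Power |
|---|---|---|
| 1 | 19 | 76–78% |
| 2 | 18 | 73–75% |
| 3 | 17 | 70–73% |
| 4 | 16 | 67–69% |
| 5 | 15 | 63–66% |

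In the last row the chance of missing a true correlation of 0.70 is 34–37%, against 20–22% at n = 20. The observed r needed to reject rises from 0.595 to 0.652. With five PR-negative patients and no PR+ dropout, n = 16 and the power is 67–69%.

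**The match at 16.** The one-sided 80% at 16 uses up 21 − 5 exactly. Both sample-size paragraphs say that one dropout is already allowed for. Taking it out leaves 15, where one-sided power is 74–77%. The coincidence therefore fails the plan's own terms.

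**The timetable.** One patient a month for 36 months has room for 36, so it holds either total. With 26 enrolled, those entered by month 36 − 12 = 24 could have a full year of follow-up if surgery is immediate. That touches recurrence only. Recurrence is exploratory, is recorded only where follow-up exists, and has a descriptive fallback in Section 12.3.3. It does not cap enrolment.

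**The case for a change.** The strongest case for a change is that the additional reading is an inference. Whoever closes enrolment needs a number, one sentence would supply it, and the summary writes PR+ for the repeat-scan group but not for the 21. The 0–8 range may describe only the Allred scale, in which case the repeated PR+ wording of the objective governs and a total of 21 would leave the test short.

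The gap in wording is real, and the power figures behind the objection are correct. But the inference is well supported. The 21 comes out of a calculation that needs 20 evaluable patients in the analysed group, so a statistician checking it would find that fewer PR+ patients do not meet it. The repeat-scan patients are expressly called a subset, whereas the PR-negative patients are introduced after the calculation is complete, as patients to be enrolled. They have their own use in Section 12.2.3. The opposite view, that PR-negative patients belong in the correlation because the operative text spans scores of 0 and 2 and nowhere excludes them, also keeps the stated power. The two reasonable ways of filling the gap both leave the primary test sound.

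**Conclusion.** No change follows. The plan omits a detail, and its own arithmetic supplies it: 21 patients in the analysed group, most naturally PR+, with up to five PR-negative patients in addition. Two-sided power is then 78–80% (80.2% exact), as stated. The fall to 67–69%, or 63–66% with a PR+ dropout, requires enrolment to close at 21 in all, PR-negative patients to be left out of the test, and all five places to be used, although the limit is a maximum and could yield none. With one such patient the figure is 76–78%.

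This rests on bivariate normality, as the planned Pearson test does, and on the two-sided version in Section 12.1.1 being the operative one, since only that version reproduces 21. The one-sided wording in the summary contradicts it; that is a separate matter and is not resolved here. A figure in Number of Subjects and the schema are not visible in the text reviewed, so a count given there could not be checked.

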## SCHEMA

## 2. INTRODUCTION

The majority of deaths due to breast cancer occur in women with estrogen receptor alpha positive (ER+) disease (2). Endocrine therapy targets the estrogen signaling pathway controlling tumor growth and is standard treatment for women with ER+ primary and metastatic breast cancer. However, endocrine therapy is effective in some but not all women with ER+ tumors. Due to the well-recognized diversity and complexity of ER signaling mechanisms, it is inevitable that some patients will have or develop disease that has circumvented standard methods for blocking ER function and have become endocrine insensitive. This important shift in receptor functionality cannot be directly measured by current clinical diagnostic approaches. Thus, a reliable test that measures functional endocrine sensitivity in a single patient is imperative and has potential for significant clinical impact.

Progesterone receptor (PR) is a classic estrogen-regulated target gene (3). Measuring changes in PR expression may be a useful pharmacodynamic biomarker for ER function and endocrine sensitivity. Howell et al. showed using tissue biopsy that changes in PR protein levels within a few weeks after initiating anti-estrogen therapy with tamoxifen in patients with locally advanced or recurrent ER+ breast cancer correlated with prolonged time to progression and improved survival (4). When analyzing the PR status using only the pretreatment biopsy, no significant differences in survival or time to progression were identified. Thus, PR can serve as a pharmacodynamic biomarker of endocrine sensitivity and ER $\alpha$  functional activity.

Tumoral expression of PR can be visualized and quantified through the use of an investigational radiolabeled progestin,  $^{18}\text{F}$ -fluorofuranyl norprogesterone (FFNP), and positron emission tomography (PET) imaging (5-10). A “first-in-human” study involving 20 patients with invasive breast cancer has been published using FFNP-PET/CT imaging (11). There were no adverse events, changes in vital signs, laboratory values or electrocardiograms, or clinically detectable pharmacologic effects. Dosimetry evaluation determined that the effective dose equivalent of FFNP is comparable to other clinically utilized PET imaging agents. FFNP uptake as measured by tumor-to-normal breast tissue ratios was greater in PR+ cancers compared to PR- cancers. Thus, FFNP-PET appears to be a feasible method of imaging PR in breast cancer patients.

A drawback of PET for imaging primary breast cancer is its limited spatial resolution. Magnetic resonance imaging (MRI), however, produces exquisitely detailed images of the breast due to its high spatial resolution. MRI evaluation of breast cancer is dependent on anatomic detail to characterize tumor morphologic characteristics and functional assessment of lesion perfusion, characterized by the time-dependent uptake and lesion enhancement with gadolinium contrast (dynamic contrast enhanced MRI). These features make breast MRI the most sensitive method for the detection of breast cancer (13). In contrast, CT does not offer the soft tissue differentiation necessary for evaluation of the breast. Thus, MRI has become the standard of care when an additional modality is necessary to evaluate for breast cancer. CT is not used in clinical practice to evaluate the breasts.

Combining PET with MRI leverages the benefits of both modalities for the evaluation of breast cancer. Simultaneously acquired MRI images assist with PET radiotracer dose reduction, which is a necessary, critical advancement for the translation of PET/MRI imaging of the breast to clinical practice. Our research team has developed and validated the imaging acquisition protocol and workflow for breast PET/MRI (14). The protocol accounts for MR attenuation correction, quantitative standardized uptake value (SUV) calculation using PET, motion correction, co-registration of the two imaging modalities, radiopharmaceutical dose reduction, and patient workflow considerations. Although this protocol was validated using F-fluorodeoxyglucose (FDG), it will be applicable for any novel molecular radiotracer to be imaged in combination with MRI, including FFNP.

It is important to validate the accuracy and reproducibility of quantitative tumor FFNP uptake measured using PET/MRI breast imaging. Further studies will be performed to test whether FFNP-PET/MRI can be used to distinguish patients with endocrine-sensitive from endocrine-resistant ER+ primary breast cancer. To the best of our knowledge, this study will be the first to investigate simultaneous breast PET/MRI imaging with FFNP for measuring PR expression in primary breast cancer.

